**16.43 Exploratory Outcomes Analyses**

16.431 **Compliance to Treatment:** Patient compliance to ibrutinib, dexamethasone, and lenalidomide will be assessed by means of self-reported and healthcare staff assessed pill count/diary. Correlation between medication adherence and disease response will be assessed.

16.432 Quality of Life (QoL): In the proposed trial, patient-reported QoL will be measured with the MD Anderson Symptom Inventory – Multiple Myeloma (MDASI-MM), which has been a validated tool. The MDASI-MM consists of 13 core items, 7 MM-specific symptom severity items and 6 interference items; the time frame for addressing symptom severity and interference is the last 24 hours. From these items, mean subscale scores have been derived: mean Core (13 core items), mean Severity (13 core items + 7 MM-specific items), and mean Interference (6 interference items); an exploratory analysis in this study will examine a 4th score, the mean Severity score for the 7 MM symptoms. Response options range from 0 (“not present”) to 10 (“as bad as you can imagine”) for the severity items and from 0 (“did not interfere”) to 10 (“interfered completely”) for the interference items. These will be completed by patients in a paper or electronic entry at baseline (within 14 days of starting treatment), at the end of cycle 1 ( $\pm$  3 days), at the end of cycle 6 ( $\pm$  3 days) and at completion of cycle 12 of treatment ( $\pm$  3 days), at any time the patient progresses while on the 3-drug regimen and is removed from the study protocol (within 14 days of removal from the study). The primary outcome of interest for this trial is the difference in the change of the mean Symptom Severity score for the Core plus 7 MM symptom items from baseline to the end of 6 cycles of therapy, and any variation reported in the MDASI-MM score at one year.

#### 16.44 Exploratory Correlative Outcomes Analyses

16.441 BTK signalosome members (BTK, PLCy2, Lyn, Fyn, Syk, BLNK, BCAP, PI3K, NFkB, NFAT, pAKT and pS6) will be profiled by MSD-based mesoscale assay (or phospho-flow) at baseline before treatment, after cycle 1 (phase II patients only), and at the time of response assessment or disease progression. BTK signalosome component expression levels will be determined from BM and/or peripheral blood. Each measure will be summarized descriptively at each time point and changes across time will be evaluated. Correlation with response to overall therapy will be assessed using Wilcoxon’s rank sum tests.

16.442 Ibrutinib has been shown to modulate T-cells populations (Th1, Th2 and T-Regs). Similarly, the combination of lenalidomide and dexamethasone is also known to act on these cell types. To understand the impact of this combination, we will conduct flow cytometry/FACS analysis to identify percentages of the immune cell populations (T-cells, NK cells, macrophages) in the bone marrow and peripheral blood at baseline before treatment, after cycle 1 (phase II patients only) and at the time of response assessment or disease progression. Each measure will be summarized descriptively at each time point and changes across time will be evaluated. Correlation with response to overall therapy will be assessed using Wilcoxon’s rank sum tests.

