Thus, it is rational to test the efficacy of ibr in MM as a single-agent as well as in combination with len+dex, especially in treatment-naive elderly or transplant ineligible patients, where a more favorable adverse event profile is desirable. Since such a combination has not been previously tested in MM, an initial phase 1 trial component with a recommended phase 2 dose (RP2D) strategy for the combination of ibr with len and dex is being proposed. After the RP2D of this combination has been determined, subsequent enrollment would be with patients initially treated with ibr and dex and after completing the first cycle of treatment with this (1 cycle=28days), len will be added. This will help provide important correlative data to explore the biological activity as well as pharmacodynamics of ibrutinib in myeloma, for which concrete data is so far lacking despite clinical trials showing efficacy.

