### 2.4 Correlative Research Objective:

- 2.41 To determine the role of members of the BTK signalosome in achievement or lack thereof of response to ibrutinib.
- 2.42 To explore biologic effects of ibrutinib on microenvironment in MM and correlate with response to treatment.
- 2.43 To evaluate pharmacodynamic measures including receptor occupancy for BTK prior to introducing lenalidomide in patients treated with ibrutinib and dexamethasone.
- 2.44 To evaluate the impact of ibrutinib on platelet aggregation.

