## 14.0 Body Fluid Biospecimens

### 14.1 Summary Table of Research Blood and Body Fluid Specimens to be collected for this Protocol

Correlative Study (Section for more information)	Mandatory or Optional	Blood or Body Fluid being Collected	Type of Collection Tube (color of tube top)	Volume to collect per tube (# of tubes to be collected)	Baseline	Every cycle	End of treatment	Process at site?	Temperature Conditions for Storage /Shipping
BTK Signalosome	Mandatory	Bone marrow aspirate	Green Top tube	5 mL (2)	Baseline/ after registration but prior to treatment	Prior to addition of len to ibr- dex* and as clinically indicated***	Confirmed disease progression	No	On dry ice
Effect of Ibr on microenvironment	Mandatory	Bone marrow aspirate	Green Top tube	5 mL (1)	Baseline/ after registration but prior to treatment	Prior to addition of len to ibr- dex* and as clinically indicated***	Confirmed disease progression	No	At room temperature
Effect of Ibr on microenvironment	Mandatory	Peripheral Blood	Green Top tube	5 mL (2)	Baseline/ after registration but prior to treatment	Every 3 cycles while patient continues on treatment**		No	At room temperature
Effect of Ibr on platelet aggregation (Platelet surface glycoprotein by flow cytometry, blood)	Mandatory	Peripheral Blood	Yellow Top tube	5 ml	Baseline/ after registration but prior to treatment	Every cycle for first 3 cycles; then every 3 cycles while patient continues on treatment for up to 12 cycles	Confirmed disease progression	Yes	At room temperature

Correlative Study (Section for more information)	Mandatory or Optional	Blood or Body Fluid being Collected	Type of Collection Tube (color of tube top)	Volume to collect per tube (# of tubes to be collected)	Baseline	Every cycle	End of treatment	Process at site?	Temperature Conditions for Storage /Shipping
Effect of Ibr on platelet aggregation Platelet aggregation study (functional)	Mandatory	Peripheral Blood	Special tubes to be supplied by heme lab	9 ml (4)	Baseline/ after registration but prior to treatment	Every 3 cycles while patient continues on treatment for up to 12 cycles	Confirmed disease progression	Yes	At room temperature

\*Phase II only

\*\*Additional samples to be drawn in-between every 3 cycles in case there is confirmed disease progression

\*\*\* Additional samples to be drawn if a bone marrow is done for confirmation of response or as otherwise clinically indicated.

ibr=ibrutinib, len=lenalidomide, dex=dexamethasone

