### 16.3 Phase II Statistical Design:

#### 16.31 Decision Rule:

In a previous study of lenalidomide and dexamethasone in patients with transplant ineligible newly diagnosed multiple myeloma, 1076 patients were treated and evaluated for response. The overall response rate in 541 patients treated with 18 cycles of lenalidomide and dexamethasone was 73%. In 535 patients who received continuous dosing of lenalidomide and dexamethasone until disease progression, the overall response rate was 75%. An increase in overall response rate for ibrutinib, dexamethasone, and lenalidomide would be of interest.

The largest success proportion where the proposed treatment regimen would be considered ineffective in this population is 65%, and the smallest success proportion that would warrant subsequent studies with the proposed regimen in this patient population is 85%. The following one-stage design with an interim analysis is based on a two-stage Simon optimum design and requires 34 evaluable patients to test the null hypothesis that the true success proportion in this patient population is at most 65%

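### Objective 2.41 asks about response to ibrutinib, but 16.441 tests signalosome markers only against three-drug response and does not link them to disease change in the pre-lenalidomide cycle

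*Combined protocol and SAP*

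**What the plan says.** Objective 2.41 is "To determine the role of members of the BTK signalosome in achievement or lack thereof of response to ibrutinib". Section 14.41 adds the aim of finding a signalosome pattern that marks lack of response or progression on single-agent ibrutinib. Objective 2.42 is worded differently: "To explore biologic effects of ibrutinib on microenvironment in MM and correlate with response to treatment".

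Phase II withholds lenalidomide until Cycle 2 (7.12). Section 1.6 gives the reason: "This will help provide important correlative data to explore the biological activity as well as pharmacodynamics of ibrutinib in myeloma". The table in 14.1 makes a marrow sample mandatory at that point in Phase II: "Prior to addition of len to ibr- dex".

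Section 16.441 profiles the signalosome at baseline, "after cycle 1 (phase II patients only), and at the time of response assessment or disease progression". It then says: "Each measure will be summarized descriptively at each time point and changes across time will be evaluated". The one response analysis is "Correlation with response to overall therapy will be assessed using" Wilcoxon rank sum tests; 16.442 uses the same sentence for immune cells. Neither section says which time point enters the test, or gives a significance level.

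Two other passages bear on the outcome. Section 16.31 cites a lenalidomide-dexamethasone trial with 73% response after 18 cycles, and for the other arm: "In 535 patients who received continuous dosing of lenalidomide and dexamethasone until disease progression, the overall response rate was 75" per cent. The note in 11.5 resets the baseline to the end of Cycle 1 for patients who progress in Cycle 1, for judging response to the three-drug combination.

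**The concern.** The outcome tested in 16.441 is not the one named in 2.41. If most patients would respond to lenalidomide and dexamethasone anyway, many patients in the responder group carry little information on whether ibrutinib worked. The re-baselining rule adds to this: a patient who progressed on ibrutinib and dexamethasone can be scored as a responder once lenalidomide is added.

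The design creates a window without lenalidomide, takes a mandatory extra marrow in it, and measures the disease at its end. The plan evaluates the marker change over that window but does not relate it to the disease change over the same window. An ibrutinib-related association could be missed, and the choice of outcome and time point is left open until the data are in.

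**Working it through.** **1. Objective against test**

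| Objective | Response it names | Response tested | Match |
|---|---|---|---|
| 2.41 (and 14.41) | to ibrutinib; single-agent in 14.41 | overall therapy (16.441) | no |
| 2.42 | to treatment | overall therapy (16.442) | yes |

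**2. The plan's own figures.** No sample size or power is stated for 16.441, so the Phase II rule (16.311, 16.312) sets the maximum n and the plausible responder split. P(stop) = P(X1 ≤ 10 | 15, p). P(promising) = sum over x = 11 to 15 of P(X1 = x) × P(X2 ≥ 26 − x | 19, p).

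- p = 0.65: 0.6481 and 0.0924 (plan 0.648 and 0.092).
- p = 0.85: 0.0617 and 0.9042 (plan 0.062 and 0.904).

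The design reproduces. Expected responders and non-responders (34p and 34(1 − p)) are 22.1/11.9 at 65%, 25.5/8.5 at 75% and 28.9/5.1 at 85%.

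**3. Wilcoxon power with no dilution.** Assumptions: normal markers, a true 1.0 SD difference, two-sided 5%. Simulated power is 0.74 (22/12), 0.64 (26/8) and 0.46 (29/5). The uneven split alone costs power.

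**4. Dilution (illustrative).** Assume a patient responds if ibrutinib-sensitive (fraction s) or, independently, if responsive to lenalidomide-dexamethasone (probability L), and that the marker is shifted only in sensitive patients. Then overall response P = 1 − (1 − s)(1 − L). Non-responders contain no sensitive patients and responders contain a fraction s/P, so the share of the shift that survives is s/P. For P = 0.85, s = 1 − 0.15/(1 − L). L = 0.73 and 0.75 are the cited rates; L = 0.65 is the plan's ineffective rate, used as a low value.

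| L | s | P | Share retained | Power, overall response | Power, sensitivity known exactly |
|---|---|---|---|---|---|
| 0.65 | 1 − 0.15/0.35 = 0.57 | 0.85 | 67% | 0.21 | 0.77 |
| 0.73 | 1 − 0.15/0.27 = 0.44 | 0.85 | 52% | 0.14 | 0.76 |
| 0.75 | 1 − 0.15/0.25 = 0.40 | 0.85 | 47% | 0.11 | 0.74 |
| 0.75 | 0.20 (assumed) | 0.80 | 25% | 0.07 | 0.56 |

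Power is for n = 34 and a 1.0 SD shift. The last column is an upper bound, since no measurement shows sensitivity exactly.

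**5. Does the Cycle 1 disease change do better?** Assume the marker correlates 0.5 with the ibrutinib effect, and a disease measure correlates r with that effect. Spearman power at n = 34, two-sided 5%:

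| r | 0.3 | 0.4 | 0.5 | 0.6 | 0.8 |
|---|---|---|---|---|---|
| Power | 0.12 | 0.18 | 0.28 | 0.37 | 0.61 |

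The two-group test on overall response (80% responding, r = 0.3 to 0.5) has power 0.09 to 0.16. Cycle 1 change therefore helps to the extent that its r exceeds that of overall depth of response. Part of the gain over the two-group test comes simply from not dichotomising.

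**6. What the window can supply.** The schedule in 4.1 has electrophoresis and free light chains on Day 1 of each cycle, so one post-baseline value is scheduled before lenalidomide. Table 11.5 requires two consecutive assessments, so a confirmed response to ibrutinib and dexamethasone is not obtainable; a percent change is.

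**The case against.** Much of the plan can be defended.

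- Section 1.71, which carries the 2.41 objective, describes the analysis as association with the response eventually seen to the treatment, and 16.441 implements that. This stands in part: rewording 2.41 would close that gap, but 14.41's single-agent aim would still have no analysis.
- A reader might infer that the Cycle 1 data go unused. They do not: 16.441 evaluates marker changes across time, and objective 2.43 covers pharmacodynamics before lenalidomide. Only the link to disease change is missing.
- A reader might extend the mismatch to 16.442. Objective 2.42 asks for response to treatment, which is what 16.442 tests. Only the hypothesis in 1.72, that the Th1 response drives ibrutinib's depth of response, goes further.
- A reader might infer circularity, because samples at response or progression are timed by the outcome. Section 16.441 lists them for profiling and does not say that they enter the Wilcoxon test. This is an ambiguity to settle, not a stated flaw.
- Cycle 1 change is a single value under weekly dexamethasone. If it tracks the ibrutinib effect no better than overall depth does, its advantage over overall depth disappears. This stands, and no particular power gain should be claimed.

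**Conclusion.** The mismatch between 2.41 (with 14.41) and 16.441 is real, and no analysis of response in the pre-lenalidomide window is specified. Dilution is likely, given the cited 73% and 75% response rates and the re-baselining in 11.5. Its size is not known: at 85% overall response the model retains 47% to 67% of a marker difference, and 25% in a less favourable case. These figures rest on independence, a shift confined to ibrutinib-sensitive patients, and assumed values of s and L.

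A reader might conclude that lenalidomide swamps the signal or that 2.41 cannot be answered at all. The documents do not support that, because they give no marker effect size, no rate of sensitivity to ibrutinib and no correlation of Cycle 1 change with ibrutinib effect. The point is minor: 16.44 is exploratory, and no decision rule, primary endpoint or secondary endpoint depends on it.

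**What to change.** In 16.441, for Phase II:

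- Add, as the analysis for 2.41, the Spearman correlation of (a) baseline markers and (b) marker change from baseline to the end of Cycle 1 with the percent change in the followed disease measure, from baseline to before lenalidomide at Cycle 2 Day 1. The measure is serum or urine M-protein, the free light chain difference, or marrow plasma cell percentage for patients followed by marrow only.
- Label this as response to ibrutinib plus dexamethasone, based on a single unconfirmed measurement.
- Keep the Wilcoxon test as the three-drug response analysis. State that it uses baseline and end-of-Cycle-1 samples, and describe samples taken at response or progression only as paired changes.

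The same Cycle 1 analysis in 16.442 is optional, for the hypothesis in 1.72. Sections 1.71 and 1.75 describe the first month as ibrutinib alone, while 7.12 schedules dexamethasone in Cycle 1; these passages must be reconciled so that the label is right.

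The cost is wording. Electrophoresis, free light chains and the extra Phase II marrow are already scheduled in 4.1; for marrow-only patients, a plasma cell percentage must be recorded from that marrow.

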### 11.1 Terms and definitions

- **Monoclonal protein:** synonyms include M-spike, M-protein and myeloma protein, paraprotein, M-component.

Serum Monoclonal protein level is quantitated using densitometry on SPEP except in cases where the SPEP is felt to be unreliable.

- Monoclonal protein migrating in the β-region (usually IgA Monoclonal protein)
- Cases in which the Monoclonal protein is so large and narrow on agarose (some specimens >4 g/dL) that they underestimate the actual immunoglobulin level (by greater than 1500 mg/dL) due to technical staining properties of the agarose gel.
- Cases in which there are multiple peaks of same Monoclonal protein (aggregates or dimers)

If SPEP is not available or felt to be unreliable (above examples) for routine Monoclonal protein quantitation, then quantitative immunoglobulin levels derived from nephelometry or turbidometry can be accepted. However, this must be explicitly reported at baseline, and only nephelometry can be used for that patient to assess response. SPEP derived Monoclonal protein values and quantitative nephelometric immunoglobulin values cannot be used interchangeably.

Urine Monoclonal protein measurement is estimated using 24-h UPEP only. Random or 24 h urine tests measuring kappa and lambda light chain levels are not reliable and are not recommended.

**FLC estimation** is currently carried out using the serum FLC assay (Freelite, The Binding Site Limited, UK). Patients with kappa/lambda FLC ratio  $<0.26$  are defined as having monoclonal lambda FLC and those with ratios  $>1.65$  as having a monoclonal kappa FLC. The monoclonal light chain isotype is considered the involved FLC isotype, and the opposite light chain type as the uninvolved FLC type.

- **Response terms:** The following response terms will be used: stringent Complete Response (sCR), complete response (CR), very good partial response (VGPR), partial response (PR), Minimal Response (MR), stable disease (SD), and progressive disease (PD).

In addition, for each response category, there will be an “unconfirmed” response category, which will be for internal use, for the purpose of guiding decision making and test ordering. These designations will be applied at the time of the first measurement at which the quantitative aspect of the response category has been satisfied without the confirmation step having been satisfied. The designation “u” will precede the standard abbreviations, and will include usCR, uCR, uVGPR, uPR, uMR, uPD.

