## 14.4 Background and Methodology

14.41 BTK signalosome: The variability in the extent of clinical response may suggest underlying adaptability of the MM clone mediated through components of the BTK signalosome. Patients with B-cell malignancies treated with ibrutinib demonstrate upregulation of p-Akt and p-Erk (downstream mediators of BTK) in some (but not all) patients and suggest that these downstream pathways may contribute to the survival of the malignant clone. They also concluded that these cells might not be dependent upon the proximal BTK pathways mediated apoptosis and thus resistant to killing by ibrutinib. To address this question we will establish the profile of BTK signalosome for each patient through determination of the mRNA (RT-PCR/ nanostring assay) and protein expression (western blot analysis) of members of the BTK signaling pathway. Samples: Bone marrow samples (2 x 5ml green top tubes) will be collected at prior to initiating the ibrutinib therapy, at the time of disease progression while on ibr therapy or if there is a lack of response noted to single-agent ibr at the time points specified in the study schema. In the form of expected results, we anticipate (a) variability in the expression and phosphorylation status of various members of BTK pathway (Syk, Lyn CD79 FYN) and their targets (ERK, AKT, NFKB and Bcl-2, Mcl-1, XIAP, MYC, CD40 and CFLAR) (b) and predict correlation of this variability with the depth of response achieved in that patient. Furthermore, this will also help identify the signalosome pattern that may suggest lack of response/progression to single-agent ibr in MM patients.

14.42 Effect of ibrutinib on MM microenvironment: In cancer redirection of host immunity from a predominant Th2 to Th1 response can deliver antitumor response. Ibr can bind to ITK, a member of the TEC-kinase family mediates TCR signaling through PLC $\gamma$ , NFAT, NF- $\kappa$ B and MAPK. This results in activation and proliferation of CD8+ cells. Our hypothesis is that ibr alters the

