Th2:Th1 balance in the blood and bone marrow microenvironment skewing towards a more Th1 profile and this may translate into its clinical efficacy. We further hypothesize that the robustness of the Th1 response will direct ibrutinib's depth of response. Blood and bone marrow will be evaluated/quantified for Th1 and Th2 cells (by flow cytometry). Changes in the cellular profile as well as respective cytokine (such as IL2, IL12, INF $\gamma$  and IL4, IL5, IL13 and IL10, respectively) will be measured (for cytokine we will use the multiplex assay). Blood (2 x 5ml green top tubes) and bone marrow samples (1 x 5ml green top tubes) will be collected at any time prior to initiating the ibrutinib therapy. Serial bone marrow samples will be collected at the time of disease progression while on ibr therapy or if there is a lack of response noted to single-agent ibr at the time points specified in the study schema. Furthermore, serial blood samples will be collected every 3 months while the patient remains on study treatment and additionally at the time of disease progression while on ibr therapy or if there is a lack of response noted to single-agent ibr at the time points specified in the study schema.

We anticipate that ibr treatment (a) will result in increase in Th1 cells both in the blood and the bone marrow with bone marrow demonstrating a higher percentage of Th1 cell activity and that (b) extent of immune cellular response will correlate with the robustness of the clinical response and that (c) the cytokine profile will mimic this cellular pattern and can be used to predict immune cellular response to ibrutinib. Identification / validation of immune restoration ability of ibr and its correlation with disease response will be a highly novel observation and will define a unique role and mechanism of ibrutinib in MM.

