## 16.0 Statistical Considerations and Methodology

### 16.1 Overview

This is a phase I/II study of a novel regimen of Ibrutinib, dexamethasone, and lenalidomide in patients with MM. The phase I portion is designed to determine the maximum tolerated dose (MTD) of ibrutinib that can be combined with lenalidomide and dexamethasone in patients with relapsed MM. The phase II portion is designed to assess the confirmed response rate of Ibrutinib, dexamethasone, and lenalidomide using a one stage phase II study design with an interim analysis in patients with transplant ineligible newly diagnosed MM.

Note: Phase II will not be initiated until after FDA review of Phase I data and approval to continue.

16.11 Primary Endpoint: The primary endpoint of the phase I portion of this trial is to assess the maximum tolerated dose (MTD). The primary endpoint of the phase II portion of this trial is the rate of confirmed response. A confirmed response is defined as a patient who has achieved an sCR, CR, VGPR, or PR on two consecutive evaluations at any time during treatment. Confirmed response will be evaluated using all cycles. All patients meeting the eligibility criteria, who have signed a consent form and have begun treatment will be evaluable for response, unless they are determined to be a major violation.

16.12 Sample Size: This phase I portion of this study is expected to require a minimum of 6 and a maximum of 24 evaluable patients. For the phase II portion, the one stage study design with an interim analysis to be used is fully described below.

A minimum of 15 and a maximum of 34 evaluable patients will be accrued total onto this phase II study unless undue toxicity is encountered. We anticipate accruing an additional 5 patients (2 phase I, 3 phase II) to account for ineligibility, cancellation, major treatment violation, or other reasons for a total of 63 patients overall.

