**16.41 Primary Outcome Analysis:**

16.411 **Definition:** The primary endpoint of this trial is the confirmed response rate. A success is defined as a sCR, CR, VGPR, or PR noted as the objective status on two consecutive evaluations at any time. All patients meeting the eligibility criteria who have signed a consent form and have begun treatment will be evaluable for response, unless they are determined to be a major violation.

16.412 **Estimation:** The proportion of successes will be estimated by the number of successes divided by the total number of evaluable patients. Ninety-five percent confidence intervals for the true success proportion will be calculated according to the approach of Duffy and Santner.

16.413 **Over Accrual:** If more than the target number of patients are accrued, the additional patients will not be used to evaluate the stopping rule or used in any decision making processes; however, they will be included in final point estimates and confidence intervals

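### The correlatives are predicted to track depth of response, but Sections 16.441 and 16.442 plan only a two-group rank-sum test with undefined groups; an ordered analysis should be added

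*Combined protocol and SAP*

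**What the plan says.** **Hypotheses.** Section 14.41 expects variability among signalosome members and goes on to "predict correlation of this variability with the depth of response achieved in that patient". Section 14.42 (and Section 1.72 in nearly the same terms) states "We further hypothesize that the robustness of the Th1 response will direct" ibrutinib's depth of response. Among its expected results, Section 14.42 adds that the "extent of immune cellular response will correlate with the robustness of the clinical response". All three are statements about a gradient.

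**Objectives.** Section 2.4 is less uniform. Objective 2.41 reads "To determine the role of members of the BTK signalosome in achievement or lack thereof of response to ibrutinib", which is a yes/no question. Objective 2.42 asks only for a correlation with response to treatment.

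**Analysis.** For both marker families, Section 16.44 plans descriptive summaries at each time point and an evaluation of change over time. For the relation with response it names a single method: "Correlation with response to overall therapy will be assessed using" Wilcoxon's rank-sum tests. It does not say which two groups are compared, or whether phase I and phase II patients are analysed together.

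**Data available.** Section 11.1 and Table 11.5 provide seven ordered grades: sCR, CR, VGPR, PR, MR, SD and PD. The only two-way response definition in Section 16 is PR or better. In Section 16.411: "A success is defined as a sCR, CR, VGPR, or PR noted as the objective status on two consecutive evaluations". On phase II size, Section 16.12 states: "A minimum of 15 and a maximum of 34 evaluable patients will be accrued total".

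**The concern.** A rank-sum test on responders against non-responders treats a stringent complete response and a bare partial response as the same outcome. It also treats a minor response and outright progression as the same. A marker that rises steadily with depth of response is then judged only on the contrast at one cut. That contrast becomes more lopsided the better the regimen works, because few patients fall below PR.

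What is at stake is the use made of mandatory samples. Marrow and blood for correlatives are a condition of entry (Section 3.19e), and phase II adds a marrow after cycle 1 for this purpose (Section 4.1, footnote g). The predictions in Section 14.4 would go without a matching test although the grades needed for one are already recorded.

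**Working it through.** **1. The plan's own figures.** The documents give no power, significance level or effect size for the correlatives. The only power table at this sample size is in Section 16.32. With 15 then 19 patients, continuing at 11 or more and declaring promise at 26 or more:

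P(promising) = Σ over x = 11 to 15 of Bin(x; 15, p) × P(Y ≥ 26 − x), with Y ~ Bin(19, p).

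This gives 0.0924, 0.4585 and 0.9042 at p = 0.65, 0.75 and 0.85 (plan: 0.092, 0.459, 0.904). The interim stopping probabilities are 0.6481, 0.3135 and 0.0617 (plan: 0.648, 0.314, 0.062). The design reproduces, so 34 patients and the 65% to 85% range are sound inputs. The 75% is the rate that Section 16.31 cites for continuous lenalidomide and dexamethasone.

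**2. Group sizes if the split is at PR.** This split is inferred from Section 16.411. Expected non-responders among 34:

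- 65%: 34 × 0.35 = 11.9, about 22 against 12
- 75%: 34 × 0.25 = 8.5, about 26 against 8
- 85%: 34 × 0.15 = 5.1, about 29 against 5

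The equivalent number of evenly split patients is 4·n₁·n₂/(n₁+n₂): 31.1, 24.5 and 17.1 respectively.

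**3. Power under a graded relation.** This is a simulation with 20,000 runs per scenario, n = 34, two-sided 5%. A latent bivariate normal with correlation ρ links marker and depth. Depth is cut into five grades (SD/PD, MR, PR, VGPR, CR/sCR). None of the following comes from the documents: the 5% level, ρ, or the assumed spread over grades in percent, which is

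- 65% response: 15/20/30/20/15
- 75% response: 12/13/32/28/15
- 85% response: 8/7/30/35/20

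| Response rate | ρ | Two-group, split at PR | Two-group, split at VGPR | Ordered test | Loss, PR split | Loss, VGPR split |
|---|---|---|---|---|---|---|
| 65% | 0.3 | 0.250 | 0.252 | 0.351 | 29% | 28% |
| 65% | 0.4 | 0.423 | 0.416 | 0.583 | 28% | 29% |
| 65% | 0.5 | 0.625 | 0.622 | 0.807 | 23% | 23% |
| 75% | 0.3 | 0.232 | 0.262 | 0.353 | 34% | 26% |
| 75% | 0.4 | 0.378 | 0.434 | 0.577 | 34% | 25% |
| 75% | 0.5 | 0.562 | 0.640 | 0.801 | 30% | 20% |
| 85% | 0.3 | 0.184 | 0.264 | 0.343 | 47% | 23% |
| 85% | 0.4 | 0.298 | 0.434 | 0.573 | 48% | 24% |
| 85% | 0.5 | 0.449 | 0.643 | 0.795 | 43% | 19% |

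Loss is 1 − (two-group power ÷ ordered power). At ρ = 0 both tests rejected in 4.4% to 5.0% of runs. A separate simulation using Kendall's tau at ρ = 0.5 gave 0.62/0.55/0.44 for the split at PR against 0.81/0.80/0.79 for the ordered test, at 65/75/85% response.

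**4. Sensitivity.**

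- *Other grade spreads at 85%* (most patients at PR, or only three levels): 0.45 against 0.73 to 0.74 at ρ = 0.5.
- *Phase I pooled* (assumed: 24 added patients, 50% response, ρ = 0.5): 0.86/0.81/0.72 for two groups against 0.95/0.93/0.92 for the ordered test. A gap remains, but it is much smaller.
- *A step rather than a gradient* (marker shifted 1.2 SD between responders and non-responders and flat within each): the order reverses, with 0.86/0.78/0.60 for two groups against 0.70/0.53/0.28 for the ordered test.

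**The case against.** The strongest defence is that the rank-sum test answers an objective that the protocol states. Objective 2.41 is about response or its absence. Section 1.71 speaks of eventual response or lack of it, and Section 14.41 also seeks the pattern that marks non-response. For that question a responder comparison is the direct test, and step 4 shows it is the better one when the marker separates the two groups without a gradient. This stands in full. A reader might infer that the rank-sum test should be replaced, or that an ordered test has no downside. The documents do not support either, because replacement would leave objective 2.41 without its matching test.

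Second, the split at PR and the set of 34 are inferences. Section 16.44 defines neither, and its restriction to phase II applies only to the sample after cycle 1. A split at VGPR reduces the loss at 75% and 85% response (not at 65%), and pooling phase I reduces it as well. One could even read the test as comparing response grades between high-marker and low-marker patients, but no marker cut-point is given. This too stands. It limits how firmly the size can be stated, and it shows that the groups need defining.

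Third, a reader might infer that most correlatives are undetectable as planned. That does not follow. No effect size is stated for any marker, and the two-group power at ρ = 0.5 is about 0.44 to 0.62, not negligible. At ρ = 0.4 even the ordered test reaches only about 0.58.

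Finally, Section 16.44 is labelled exploratory and claims no power. That bears on the severity, not on the mismatch between hypothesis and method.

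**Conclusion.** The mismatch holds on the text alone: the predictions in Sections 1.72, 14.41 and 14.42 are graded, and no planned analysis relates a marker to response grade. The size depends on assumptions. With groups split at PR, 34 phase II patients, a graded relation of correlation 0.3 to 0.5 and a two-sided 5% level, the split gives up roughly one quarter of the power at 65% response and up to about one half at 85%. The loss is smaller if phase I patients are pooled or, at the higher response rates, if the cut is at VGPR. It turns into an advantage if the marker changes only as a step at PR. The primary endpoint, its decision rule and its error rates are unaffected. This is a cheap improvement to an exploratory analysis (severity: nice to have), not a flaw that threatens the trial's conclusions.

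**What to change.** In Sections 16.441 and 16.442:

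1. Add an ordered analysis of each marker across best confirmed response grade (Kendall's tau-b or Jonckheere-Terpstra) and name it as the test of the depth-of-response hypotheses.
2. Keep the rank-sum test for objective 2.41 and state its two groups, PR or better against less, in line with Section 16.411.
3. State whether phase I and phase II patients are pooled for each comparison.

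No new data are needed. The cost is one further exploratory test per marker, which should be reported as such, and a definition of the best-response variable. That definition must cover at least two cases: the MR row of Table 11.5 gives no criterion for patients measurable only by free light chain or only by marrow, and Section 11.5 resets the baseline for patients who progress during cycle 1. In practice this means a sentence or two in each subsection plus a short definition.
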